## 7.6 Software

SAS® software version 9.4 or higher will be used to perform most or all statistical analyses.

## 8 STATISTICAL METHODS OF ANALYSIS

### 8.1 General Principles

The statistical analyses will be reported using summary tables, figures, and data listings. Statistical tests will be 2-sided at the alpha=0.05 significance level and 2-sided 95% confidence interval will be used. All p-values will be presented as nominal p-values. No adjustment on multiplicity will be made. Continuous variables will be summarized with means, standard deviations, standard errors, medians, Q1, Q3, minimums, and maximums. Categorical variables will be summarized by counts and by percentages of subjects in corresponding categories. No imputation on missing data will be made, unless stated otherwise. All data obtained from the CRFs as well as any derived data will be included in data listings.

The Week 24 analysis will be performed when all patients enrolled in the study have completed the Week 24 visit or have discontinued the study. The final analysis will be conducted when all patients enrolled in the study have completed the Week 72 visit or have discontinued the study.

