## 1 INTRODUCTION

The purpose of this statistical analysis plan is to provide details of the statistical analyses that have been outlined within the original UX023-CL203 Protocol dated 05 September 2014. The data collected in this study will evaluate the safety and pharmacodynamics of KRN23 in adult subjects with X-Linked Hypophosphatemia.

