### 3 STUDY DESIGN

#### 3.1 Overall Study Design and Plan

This study is a Phase 2b, open-label, long-term extension study of the completed studies KRN23-INT-001 and KRN23-INT-002 in adult subjects with XLH. The study population will consist of approximately 25 eligible subjects who participated in Kyowa Hakko Kirin Pharma, Incorporated's study KRN23-INT-001 or study KRN23-INT-002 (received at least 2 doses of KRN23). Subjects who were discontinued from KRN23-INT-001 or KRN23-INT-002 due to a TEAE classified as possibly or probably related to treatment may be eligible for participation in this study based on the clinical judgment of the investigator with agreement from the sponsor. The study will be conducted over 72 weeks to assess the long-term safety, immunogenicity, PD, and clinical efficacy of KRN23.

The starting dose of KRN23 at Baseline (Week 0) in this study will be individual for each subject, i.e., the same as a subject's last dose in studies KRN23-INT-001 or KRN23-INT-002 (0.30, 0.60, or 1.0 mg/kg). Dosing will occur at the clinic and the volume will be based on the weight obtained on Day 0.

Up to Week 12, individual subjects who have not reached serum phosphorus levels above the lower limit of normal (LLN; 2.5 mg/dL) at the end of the dose interval may have their doses titrated every 4 weeks to a maximum dose of 1.0 mg/kg based on fasting trough serum phosphorus levels. Doses may be titrated downward if at any point the serum phosphorus level increases above the upper limit of normal (ULN; 4.5 mg/dL). KRN23 injections will be repeated every 4 weeks for the duration of the study (from Week 0 through Week 68), and weight will be reassessed periodically for dose volume adjustments as needed.

A complete schedule of events is included in [Appendix 6](#).

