#### 3.2 Study Duration

The planned duration of treatment in this study will be 72 weeks.

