#### 8.1.1 Repeated Measure Model: General Estimating Equations

When the sample size and number of observations allow it, the change from baseline over time and the binary endpoints over time will be analyzed using a generalized estimation equation (GEE) model that includes time as the categorical variable and adjusted for baseline measurement. The covariance structure that will be used for the GEE model is compound symmetry which specifies constant variance for the assessments and constant covariance between the assessments over time. If the compound symmetry covariance structure leads to non-convergence, Quasi-Likelihood Information Criterion (QIC) will be used to select the best covariance structure. Model based estimates of the changes from baseline and corresponding 95% confidence intervals will also be provided along with p-values for assessing statistical significance.

The p-value for testing the statistical significance of the change from the baseline to week 24 (for the interim analysis) and to week 72 (for the final analysis) assessments will be provided for changes from baseline in primary PD endpoints, selected safety endpoints (eGFR, creatinine, amylase), PRO endpoints (BPI, WOMAC, SF-36) and clinical outcomes endpoints (6MWT, percent predicted 6MWT, TUG).

For week 24 analysis, only measurements up to week 24 will be included in the model. For final analysis (week 72), all measurements will be included in the model.

If the number of observations are insufficient for analyses using a GEE model, a descriptive summary will be provided, and analyses using observations at a single time point, such as paired t-test or nonparametric methodologies, will be considered.

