## 8.8 Endpoints

### 8.8.1 Pharmacodynamic Endpoints

The number and proportion of subjects with serum phosphorus level in the normal range ( $\geq 2.5$  and  $< 4.5$ ) at each time point will be provided, along with the two-sided 95% confidence intervals, obtained using the GEE model described in Section 8.1.1. An overall summary of the number and proportion of patients who ever reached the normal range over the duration of the study will also be provided. Additional analyses of serum phosphorus including observed values, change from baseline, percent change from baseline over time will be summarized.

For the final analysis, the primary PD endpoints at all post-baseline visits will be compared to baseline using the GEE model described in Section 8.1.1, and the primary statistical comparison will be between the levels at baseline and week 72.

For the interim analysis, the primary PD endpoints at all post-baseline visits prior or at week 24 for all patients will be compared to baseline using the GEE model, and the primary statistical comparison will be between the levels at baseline and week 24.

For all primary PD endpoints descriptive statistics of observed values and of changes from baseline at each visit will be provided.

Graphs showing the change over time in key PD parameter for both observed measure and the change from baseline will be provided. The relationship between various PD parameters as well as KRN23 concentrations may be examined.

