## 10 APPENDICES

### Appendix 1: UX023-CL203 Efficacy Endpoint Summary Table

Test / Instrument	Eligible Study Population	Endpoint	Pharmacodynamics, efficacy or safety endpoint	Timepoints for Assessment	Statistical approach at week 24 analysis	Statistical approach at week 72 analysis
PD	PD Analysis Set	Change from baseline in serum phosphorus	Pharmacodynamics	Baseline, Weeks 2, 4, 6, 8, 10, 12, 24, 26, 28, 36, 38, 40 48, 50, 52, 60, 72/ET	GEE Model	GEE Model
PD	PD Analysis Set	Percent change from baseline in serum phosphorus	Pharmacodynamics	Baseline, Weeks 2, 4, 6, 8, 10, 12, 24, 26, 28, 36, 38, 40 48, 50, 52, 60, 72/ET	GEE Model	GEE Model
PD	PD Analysis Set	Proportion of subjects with serum phosphorus level in the normal range	Pharmacodynamics	Baseline, Weeks 2, 4, 6, 8, 10, 12, 24, 26, 28, 36, 38, 40 48, 50, 52, 60, 72/ET	GEE Model	GEE Model
PD	PD Analysis Set	Change from baseline in iPTH	Pharmacodynamics	Baseline, Weeks 12, 24, 36, 48, 72	GEE Model	GEE Model
PD	PD Analysis Set	Change from baseline in Total FGF23	Pharmacodynamics	Baseline, Weeks 4, 8, 12, 24, 28, 36, 40, 48, 72	GEE Model	GEE Model
PD	PD Analysis Set	Change from baseline in Free FGF23	Pharmacodynamics	Baseline, Weeks 4, 8, 12, 24, 28, 36, 40, 48, 72	GEE Model	GEE Model
PD	PD Analysis Set	Change from baseline in 1,25(OH) 2 D	Pharmacodynamics	Baseline, Weeks 12, 24, 36, 48, 72	GEE Model	GEE Model

Test / Instrument	Eligible Study Population	Endpoint	Pharmacodynamics, efficacy or safety endpoint	Timepoints for Assessment	Statistical approach at week 24 analysis	Statistical approach at week 72 analysis
PD	PD Analysis Set	Change from baseline in 2-hr urine parameters (TmP/GFR, calcium, creatinine, calcium/creatinine ratio, phosphorus)	Pharmacodynamics	Baseline, Weeks 12, 24, 36, 48, 72	GEE Model	GEE Model
PD	PD Analysis Set	Change from baseline in 24-hr urine parameters (calcium, calcium/creatinine ratio, creatinine, phosphorus, phosphorus/creatinine ratio)	Pharmacodynamics	Baseline, Weeks 12, 24, 36, 48, 72/ET	GEE Model	GEE Model
PD	PD Analysis Set	Change from baseline in fractional excretion of phosphorus	Pharmacodynamics	Baseline, Weeks 12, 24, 36, 48, 72/ET	GEE Model	GEE Model
PD	PD Analysis Set	Change from baseline in bone biomarkers (ALP, BALP, CTx, P1NP)	Pharmacodynamics	Baseline, Weeks 24, 48, 72/ET	Paired t-test	GEE Model

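### The supplied SAP still ends at Week 72 (stated duration, final-analysis trigger, visit tables), while the current protocol treats for 156 to 184 weeks

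*SAP*

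**What the plan says.** SAP Section 1 ties the plan to the "statistical analyses that have been outlined within the original UX023-CL203 Protocol dated 05 September 2014". The sections that follow describe that version of the study:

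- Section 3.1: "The study will be conducted over 72 weeks to assess the long-term safety, immunogenicity, PD, and clinical efficacy of KRN23".
- Section 3.2: "The planned duration of treatment in this study will be 72 weeks".
- Section 8.1, the trigger: "The final analysis will be conducted when all patients enrolled in the study have completed the Week 72 visit or have discontinued the study".
- Section 8.1.1 places the final-analysis p-values at Week 72 and adds: "For final analysis (week 72), all measurements will be included in the model".
- Section 8.8.1, for the final analysis of primary PD endpoints: "the primary statistical comparison will be between the levels at baseline and week 72".
- Appendix 1 names no time point after Week 72. The bone-marker row, for example, reads "Baseline, Weeks 24, 48, 72/ET". The Appendix 6 schedule ends at Week 72 as well.

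The current protocol (Amendment 2) gives a treatment range of 156 to 184 weeks in Section 7.4.5. Sections 7.5.1.1, 7.5.2 and 7.5.3.7 to 7.5.3.10 continue PD, serum KRN23, anti-drug antibody (ADA), renal ultrasound, ECHO and ECG assessments at Weeks 96, 120 and 144 and then 24-weekly to EoT. Section 7.5.1.2.1 continues radiographs to EoT until lesions resolve. Section 7.5.1.2.2 runs BPI and SF-36 to Week 144. WOMAC, 6MWT and TUG end at Week 72 in both documents.

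**The concern.** Long-term safety, PD and immunogenicity are the primary objectives (Protocol Section 6), and Protocol Section 7.6 leaves the detailed methods to the SAP. A final analysis tied to the last Week 72 visit closes the analysis on the earlier and shorter study. The trigger is therefore a wrong rule for the current design and not just a missing detail. If it is not amended, the timing of the real final analysis, its visit set and any later contrast would be settled after open-label data had been seen.

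Three smaller points are connected:

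- KRN23 concentration is a protocol endpoint (Section 7.6.1.3), but the SAP lists no such endpoint and says only: "The relationship between various PD parameters as well as KRN23 concentrations may be examined".
- SAP Section 7.5 summarizes by the visit number in the database, whereas Protocol Table 2.2 lets the EoT visit number differ between subjects.
- Protocol Section 7.6.3 plans no interim analyses, while the SAP plans one at Week 24. Under the current duration the Week 72 analysis is interim too.

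**Working it through.** **The protocol's own figures.** With a dose every 4 weeks from Week 0 to the visit before EoT, the number of doses is T/4. For T = 184 this is 184/4 = 46, the maximum stated in the synopsis. Adding the 8-week safety call gives 156 + 8 = 164 and 184 + 8 = 192 weeks, the study duration in Section 7.1. The current protocol is consistent on these points.

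**Treatment time after Week 72**, as (T − 72)/T:

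- 156-week subject: 84/156 = 53.8%
- 184-week subject: 112/184 = 60.9%

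In doses, the SAP's schedule (Weeks 0 to 68) holds 72/4 = 18. The current protocol holds 156/4 = 39 to 46.

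**Scheduled post-baseline time points after Week 72.** I take the later visits as Weeks 96, 120, 144 and EoT for a 156-week subject (4), with Week 168 added for a 184-week subject (5). The share is later/(to Week 72 + later).

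| Assessment | Post-baseline points to Week 72 | 156 weeks | 184 weeks |
|---|---|---|---|
| Serum phosphorus | 17 | 4/21 = 19.0% | 5/22 = 22.7% |
| FGF23 | 9 | 4/13 = 30.8% | 5/14 = 35.7% |
| ADA | 6 | 4/10 = 40.0% | 5/11 = 45.5% |
| TmP/GFR, urine, iPTH, 1,25(OH)2D | 5 | 4/9 = 44.4% | 5/10 = 50.0% |
| Bone markers, ECHO, ECG, renal ultrasound | 3 | 4/7 = 57.1% | 5/8 = 62.5% |
| Serum KRN23 (no baseline sample) | at most 4 | at least 4/8 = 50.0% | at least 5/9 = 55.6% |
| BPI, SF-36 (to Week 144) | 5 | 3/8 = 37.5% | 3/8 = 37.5% |

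The KRN23 shares are minimums because sampling could begin later than Week 24, pending approvals. Radiographs follow the TmP/GFR row as a maximum, because they stop when lesions resolve.

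**Date of the trigger.** Counting back from 30 September 2018, 184 and 156 weeks give entry from 22 March 2015 to 4 October 2015. The last Week 72 visit then falls on 19 February 2017, when the first subject is at Week 100. So a few subjects could have a Week 96 visit at the trigger, and no one could have a later one.

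**What covers later data.** SAP Section 8.8.1 compares the primary PD endpoints with baseline by GEE at every post-baseline visit, and Section 8.1.1 puts all measurements in the final model. Neither clause names a last week of its own. Protocol Sections 7.6.2.3 (all available data), 7.6.2.5 (PD summaries), 7.6.2.6 (GEE for change from baseline, with PROs to Week 144) and 7.6.2.7 (KRN23 summaries) supply the rest. None of this moves the SAP's trigger, and no analysis can use measurements that have not yet been taken.

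**The case against.** The strongest reply is that this is version lag. The SAP amendment of 27 April 2016 precedes Protocol Amendment 1 (9 May 2016) and Amendment 2 (2017), and Protocol Section 7.6.2.1 requires SAP approval only before database lock. That stands. The SAP was not wrong when written, and the documents cannot show that no later version exists.

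The study is also exploratory and unpowered, with nominal p-values. That stands too, and nothing here rests on power.

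A reader might infer more than the documents support:

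- *Data after Week 72 have no analysis plan.* The GEE clauses and protocol sections set out above cover them once the trigger is corrected.
- *The Week 72 PD contrast is itself a defect.* It is the prespecified contrast and should be kept. What is missing is a later one beside it.
- *Every subject would have 84 weeks of treatment left at the trigger.* That holds only when Amendment 2 is applied to February 2017. Amendment 1 was then in force, with EoT at Week 144, which left 144 − 100 = 44 to 144 − 72 = 72 weeks.
- *Safety reporting would be frozen at Week 72.* Protocol Section 7.6.2.3 calls for all available data, and the SAP's definition of treatment-emergent events (Section 8.6.1) has no week limit.

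On the linked points, Protocol Section 7.6.2.7 already plans KRN23 summaries, and how EoT is coded in the database is unknown. The conflict over interim analyses would exist without the extension. These are secondary.

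**Conclusion.** The concern holds for the SAP as supplied. Its stated duration, final-analysis trigger, named final p-value time point and visit tables belong to a 72-week study, and the current protocol describes one of 156 to 184 weeks. Measured against Amendment 2, 54% to 61% of planned treatment time falls after Week 72. So do 19% to 23% of post-baseline phosphorus time points, rising to 57% to 63% for bone markers, ECHO, ECG and renal ultrasound.

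These shares assume full follow-up and the visit pattern stated above. They describe where planned data fall. They are not an estimate of bias or of data that will be lost. The trigger is the part that must change before database lock, because following it would cut the final analysis short of the long-term primary objectives.

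**What to change.** Before database lock, amend the SAP to Protocol Amendment 2:

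1. In Sections 3.1, 3.2, 8.1 and 8.1.1, trigger the final analysis after the last subject's EoT visit or last safety call, and include all safety, ADA and PD data to that point.
2. Extend Appendix 1 and the schedule to Weeks 96, 120 and 144 (Week 168 descriptively) and EoT for the assessments still collected. Take BPI and SF-36 to Week 144, and leave WOMAC, 6MWT and TUG at Week 72.
3. Keep baseline versus Week 72 as the prespecified primary PD contrast. Report Week 144 as an additional long-term contrast, labeled as added after Week 72 data existed. The label does not remove the post hoc element, but it makes it visible.
4. List KRN23 concentration as an endpoint with descriptive summaries by visit, and summarize a completer's EoT visit separately.
5. Call the Week 72 analysis interim, and reconcile Protocol Section 7.6.3 with the Week 24 and Week 72 analyses.

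The cost is one SAP amendment, one protocol sentence and additional table rows. No new data collection is needed.

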#### 8.1.1 Repeated Measure Model: General Estimating Equations

When the sample size and number of observations allow it, the change from baseline over time and the binary endpoints over time will be analyzed using a generalized estimation equation (GEE) model that includes time as the categorical variable and adjusted for baseline measurement. The covariance structure that will be used for the GEE model is compound symmetry which specifies constant variance for the assessments and constant covariance between the assessments over time. If the compound symmetry covariance structure leads to non-convergence, Quasi-Likelihood Information Criterion (QIC) will be used to select the best covariance structure. Model based estimates of the changes from baseline and corresponding 95% confidence intervals will also be provided along with p-values for assessing statistical significance.

The p-value for testing the statistical significance of the change from the baseline to week 24 (for the interim analysis) and to week 72 (for the final analysis) assessments will be provided for changes from baseline in primary PD endpoints, selected safety endpoints (eGFR, creatinine, amylase), PRO endpoints (BPI, WOMAC, SF-36) and clinical outcomes endpoints (6MWT, percent predicted 6MWT, TUG).

For week 24 analysis, only measurements up to week 24 will be included in the model. For final analysis (week 72), all measurements will be included in the model.

If the number of observations are insufficient for analyses using a GEE model, a descriptive summary will be provided, and analyses using observations at a single time point, such as paired t-test or nonparametric methodologies, will be considered.

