Skeletal abnormalities of osteomalacia (rickets) often manifest in the first 2 years of childhood (e.g., bowed legs) when lower extremity bowing becomes evident with the onset of weight bearing; however, the disorder may go undiagnosed until adulthood. The initial presenting complaint in adults may be enthesopathy (calcification of the tendons, ligaments, and joint capsules) (Ruppe 2012). There is a great deal of variability in the manifestations of XLH. In the mildest cases, only hypophosphatemia is evident (Holm et al. 2012). In more severe cases, adult patients with XLH may suffer from bone pain and osteomalacia; increased risk of bone fractures; joint abnormalities and joint pain; osteoarthritis, and enthesopathy (Ruppe 2012); (Tenenhouse et al. 2001); (Reid et al. 1989). Diagnostic testing characteristically reveals low serum phosphate concentration and reduced tubular resorption of phosphate corrected for glomerular filtration rate (TmP/GFR). Additionally in adults, the normal physiologic response to hypophosphatemia of an elevation of 1,25(OH)₂D is absent; serum calcium and alkaline phosphatase (ALP) are within the normal range; and parathyroid hormone (PTH) is normal to slightly elevated. (Ruppe 2012) For definitive evidence of renal phosphate wasting, a 2-hour fasting urine specimen as well as a blood sample collected at the

midpoint of the urine collection period are used to calculate the percent tubular reabsorption of phosphate (TRP) and to determine the tubular threshold maximum for phosphate (Carpenter et al. 2011).

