## 5 DEFINITIONS AND DERIVED EFFICACY VARIABLES

### 5.1 Baseline

Baseline is defined as the last non-missing measurement taken prior to the first dose of study drug administration in CL203 study.

Note that all subjects enrolled in this study received at least 2 doses of KRN23 in Kyowa Hakko Kirin Pharma, Incorporated's study KRN23-INT-001 or study KRN23-INT-002; however, since a minimum of 21 months separated the last dose in KRN23-US-001/002 studies and the first dose in this study, values measured in KRN23-INT-001 or KRN-INT-002 studies will not serve as baseline values for this study.

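### The per-visit 95% interval for the normal-range proportion comes from a GEE that yields no usable interval when all or none of about 20 subjects are in range

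*SAP*

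**What the plan says.** SAP 8.8.1 reports the number and proportion of subjects in the normal serum phosphorus range at each time point, "along with the two-sided 95% confidence intervals, obtained using the GEE model described in Section 8.1.1". SAP 8.1.1 says that "the change from baseline over time and the binary endpoints over time will be analyzed using a generalized estimation equation (GEE) model", with time as a categorical term, adjustment for baseline, and a compound symmetry covariance. It names no link function, standard-error type, small-sample correction or reference distribution.

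Three provisions in SAP 8.1.1 deal with difficulty in fitting:

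- The opening sentence makes the GEE conditional on there being enough subjects and observations, without a threshold.
- "If the compound symmetry covariance structure leads to non-convergence, Quasi-Likelihood Information Criterion (QIC) will be used to select the best covariance structure".
- "If the number of observations are insufficient for analyses using a GEE model, a descriptive summary will be provided". Single-time-point methods, with a paired t-test and nonparametric methods as examples, are then to be considered.

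Appendix 1 assigns the GEE to the endpoint "Proportion of subjects with serum phosphorus level in the normal range" at both the Week 24 and Week 72 analyses. SAP 8.8.1 also plans a separate overall summary of subjects who were in range at least once during the study; no GEE interval is attached to that summary.

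**The concern.** The proportion of subjects reaching normal serum phosphorus is a primary objective (Protocol 6, SAP 2.1). With about 20 subjects, a visit at which every subject is in range is a realistic and favourable outcome. It is also the outcome for which a model on the logit scale has no finite estimate. The pharmacodynamic table could then show a blank, an interval covering the whole scale, or an interval of no width that claims certainty from 20 people. The last is the worst, because some of these fits report convergence and nothing in the plan would flag them.

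**Working it through.** **Inputs.** Two-sided 95% level (SAP 8.1). n = 20 (Protocol synopsis and 7.1); SAP 3.5 says about 25. Model form from SAP 8.1.1. The link is not stated: logit is assumed and identity also checked. True proportions and correlations are not given and are assumed. The documents state no interval or power figure to reproduce.

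**Step 1: the estimate at the boundary.** Under a logit link with independence, the equation for a visit's parameter sets the sum of fitted probabilities equal to the number in range. At 20/20 that sum is 20, so every fitted probability must be 1 and the logit is infinite, with or without a baseline term. Under compound symmetry with complete data and no baseline term, each fitted visit proportion again equals the observed one, with the same result. Compound symmetry with a baseline term was examined by fitting (Step 2). Under an identity link, p(1 − p)/n = 1 × 0/20 = 0, so the interval is 100–100%, or 0–0% at 0/20.

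One subject out of range restores a finite interval. At 19/20, the simple one-visit logit is ln 19 = 2.944 and its SE is 1/√(20 × 0.95 × 0.05) = 1.026. The limits 2.944 ± 1.96 × 1.026 = 0.933 to 4.955 convert to 71.8–99.3%. The failure is therefore confined to all-or-none visits.

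**Step 2: what software returns.** Simulated logit GEE fits, n = 20, baseline-adjusted, in Python statsmodels (SAS output may differ).

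- 120 data sets, 7 visits, last visit set to 20/20. Compound symmetry failed to converge in 86. The other 34 gave 0–100%, a diverged fit, or sandwich limits of 98.8–100% or narrower. Independence gave 0–100% with model-based SEs and 100–100% with sandwich SEs in all 120.
- Separate 5-visit fits with one all-in-range visit. Compound symmetry with the sandwich SE reported convergence with a logit of 506 and a missing SE. AR(1) with the sandwich SE converged with limits of about 0–100%. A none-in-range visit under compound symmetry reported convergence with SE 0 and limits 0–0%.
- A further set of refits gave the same kinds of result, including one interval of 30–100%.

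The exact interval at 20/20 is 83.2–100%. Changing the working covariance, which is all the QIC rule does, did not cure the problem.

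**Step 3: how likely it is.** The chance that all n subjects are in range at a given visit is p^n.

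| True proportion | n = 20 | n = 25 |
|---|---|---|
| 0.80 | 0.80^20 = 1.2% | 0.4% |
| 0.90 | 0.90^20 = 12.2% | 7.2% |
| 0.95 | 0.95^20 = 35.8% | 27.7% |

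**Step 4: exact limits.** At 20/20 the Clopper-Pearson lower limit is 0.025^(1/20) = 0.832; at 0/20 the upper limit is 1 − 0.832 = 0.168. At 19/20 the limits are 75.1–99.9%, and at 18/20 they are 68.3–98.8%. With 25 subjects, 25/25 gives 86.3–100%.

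**Step 5 (secondary): mean changes.** The target is the change at the observed mean baseline, with n = 20, exchangeable correlation 0.3–0.9 and equal SDs. Two-sided error is 7.2–7.6% with an uncorrected sandwich SE and normal limits, 5.2–5.7% with a model-based SE and normal limits, and 4.7–5.1% with a Kauermann-Carroll SE and t on 18 df. In an assumed scenario with rising variance and decaying correlation, the model-based interval covered 85.6–86.7%.

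**The case against.** **The plan has an escape clause.** The GEE applies only if the data allow it, and the fallback list is open enough to admit an exact interval. This is partly right: an analyst could reach a sensible answer. But the opening condition has no threshold, the fallback is triggered by too few observations when at 20/20 all 20 are present, and no interval for a proportion is named.

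**Little information is lost.** This stands. The count and percentage are reported, so any reader can compute 83.2–100% from 20/20.

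**Stronger readings that the documents do not support:**

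- *The primary PD endpoint fails.* SAP 4.2 and Protocol 7.6.1.2 word that endpoint as being in range at any time after dosing, and the matching overall summary is separate. Only the per-visit proportion is affected.
- *The Baseline interval will fail at 0/20.* A low baseline count is plausible: the Protocol says of XLH that "Diagnostic testing characteristically reveals low serum phosphate concentration", and SAP 5.1 notes that "since a minimum of 21 months separated the last dose in KRN23-US-001/002 studies and the first dose in this study". But Appendix 1 lists Baseline in an assessment-schedule column, even for change-from-baseline endpoints, and SAP 8.1.1 uses baseline as a covariate. That does not establish a planned Baseline interval, and no baseline values are given.
- *A 20/20 visit is close to certain over 17 visits.* With a constant true proportion of 0.90, the simulated chance of at least one by Week 72 is 60–89%, depending on correlation. This is illustrative only: Weeks 2, 6, 10, 26, 38 and 50 fall mid-interval while the others are at the end of the dosing interval, and upward titration is allowed to Week 12. If only those six were at 0.90, and independent, and the rest well below, it would be 1 − (1 − 0.1216)^6 = 54%.
- *The mean-change intervals are too narrow as planned.* The SAP never says which SE it uses. The model-based version is near nominal when compound symmetry is true.

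**Conclusion.** The point holds for the per-visit proportion. As written, SAP 8.8.1 produces no usable 95% interval at any visit with all or none of the subjects in range, and no other rule in SAP 8.1.1 repairs it. Under assumed true proportions of 0.80 to 0.95, a given visit has a 1.2% to 35.8% chance of being 20/20; the conclusion is the same for 25 subjects. It rests on a logit or identity link.

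The consequence is limited to stated precision. The study is exploratory, p-values are nominal, counts are reported, and no decision depends on the interval. It should be corrected because the endpoint serves a primary objective and the repair is simple. The mean-change issue is secondary and conditional: coverage of about 92–93% at n = 20 if, and only if, an uncorrected sandwich SE with normal limits is used. The Week 24 paired t-tests (6MWT, TUG, bone biomarkers) are untouched.

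**What to change.** In SAP 8.8.1, replace the GEE-derived interval for the normal-range proportion with exact (Clopper-Pearson) two-sided 95% limits at each reported time point, using subjects with a value at that visit as the denominator. This costs SAP wording and code only. The limits will be somewhat conservative at visits where the GEE would have fitted.

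Optionally, in SAP 8.1.1, state the SE for the mean-change GEE. If it is the empirical one, use a small-sample correction such as Kauermann-Carroll with a t reference on about n − 2 df, and say that the interval refers to the change at the observed mean baseline. Intervals become about 11% wider than with the uncorrected sandwich and normal limits. Readers who want the unadjusted mean change can rebuild a paired interval from the planned tables: "Continuous variables will be summarized with means, standard deviations, standard errors, medians, Q1, Q3, minimums, and maximums". No protocol change is needed.
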